8.1.3. Other Analysis

Subgroups will be defined based on the following:

- Baseline Age category (3 years to <6 years, 6 years to <9 years, 9 years to <12 years, and 12 years to 14 years)
- Baseline Age category (ages 6 to 14 only)
- Baseline Age category (ages 3 to <12 years)
- Baseline SE (0.50 D to 3.0 D and >3.0 D to 6.0 D)
- Baseline SE (\geq 1.0 D only)
- Parental History of Myopia
 - No Parental History of Myopia (including unknown)
 - At least one parent with Myopia
- Ocular medical history (progression of SE vs. no progression of SE) within past 12 months
 - Participants with history of at least 0.5 D
 - Participants with history of progression of at least 1.0 D
- Iris Color (dark vs light)
- Region (Europe vs United States)
- Race (Caucasian (white) vs Indian vs Asian (Non-Indian) vs Non-Asian)
- Sex (Male vs Female)
- Average Time Outdoors (\leq Median Average Time Outdoors, $>$ Median Average Time Outdoors)
- Average Time Near Work (\leq Median Average Time Near Work, $>$ Median Average Time New Work)

The primary efficacy endpoints will be analyzed separately for these subgroups using the FAS. The study is not powered for subgroup analysis; these analyses will be considered descriptive only. Forest type plots will be presented for the EMA and FDA primary efficacy endpoints and key secondary endpoints. The subgroup analyses will be performed using the same multiply imputed data as for the primary efficacy analyses.

For the annual progression rate efficacy endpoint, the mean and standard errors of annual progression rate will be calculated by imputation for each treatment arm by subgroup and the values combined via MIANALYZE to present the pooled estimate and corresponding 95% CI for each subgroup by treatment

For the confirmed progression efficacy endpoint, the proportion of participants with > 0.75 D progression and ASE [$\sqrt{(p(1-p)/n)}$] will be calculated by imputation for each treatment arm by subgroup and the values combined via MIANALYZE to present the pooled estimate and corresponding 95% CI for each subgroup by treatment. Point estimates and CIs will be converted to percentages in the summary outputs (i.e., proportion * 100). For small subgroups, where there is no missing data or the imputed results are the same for all imputations (no variance between imputed sets), analysis will be performed on one dataset.

Additionally, an analysis on annual progression rate of myopia by eye at Month 24 with the same MMRM model as the primary analysis will be performed. For this analysis, observations after use of prohibited or escape medications will be censored. Observations post treatment discontinuation due to a related AE will also be censored. Observations after study discontinuation will not be imputed.

8.2. Secondary Efficacy Endpoints

The hypothesis testing of secondary endpoints will be conducted using a gatekeeping procedure based on a closed fixed-sequence test order and will be applied separately for the EMA and FDA submissions. The order of testing of secondary efficacy endpoints is defined in Section 3.3. For each endpoint, except for the EMA submission Subgroup analyses as detailed below, the truncated Hochberg adjustment, if required, will be applied if more than one dose of SYD-101 is to be compared to vehicle in order to control type I error for multiple comparisons for each endpoint.

The proposed procedure is detailed below.

- For the primary efficacy endpoint, statistical significance will be achieved for both dose comparisons if both comparisons have p-values < 0.045 [based on truncation $\alpha \times (1+\gamma)/2$]. If one dose comparison has a p-value ≥ 0.045 , then the other dose comparison p-value must be less than 0.025 [$\alpha/2$] to be significant.
- The key secondary efficacy endpoint will be assessed for statistical significance dependent on the prior primary efficacy endpoint comparison outcomes.
 - If both dose comparisons were considered statistically significant for the primary efficacy endpoint, then the key secondary efficacy endpoint will be assessed at $\alpha = 0.05$ and statistical significance will be assessed as per the primary efficacy endpoint. (e.g., both comparisons are significant if both p-

values < 0.045 , otherwise if one p-value ≥ 0.045 , the other much be < 0.025 to be significant.)

- If only one dose comparison was considered statistically significant for the primary efficacy endpoint, then for the key secondary efficacy endpoint, only that dose comparison will be assessed for statistical significance and the comparison will be statistically significant for p-value < 0.005 [based on truncation $\alpha \times (1-\gamma)/2$]. The dose comparisons for all subsequent endpoints of the significant dose will be assessed at 0.005. The other dose comparison for the endpoint (and all subsequent endpoints for the non-significant dose) will be considered descriptive/nominal.
- If neither dose comparison was statistically significant for the primary efficacy endpoint, then both dose comparisons for the key secondary efficacy endpoint (and all subsequent endpoints) will be considered descriptive/nominal.
- The steps above for the key secondary efficacy endpoint will be repeated for each subsequent secondary endpoint as applicable. If both dose comparisons are significant for all endpoints, the last secondary endpoint will utilize the untruncated Hochberg procedure with $\alpha = 0.05$.

The gatekeeping procedure above will be applied for all primary and secondary endpoints in the FDA submission.

The gatekeeping procedure for the EMA submission is the same as described above through Endpoint 5 (time to progression of myopia), namely a truncated Hochberg procedure is used to test both doses for each endpoint. For Secondary Endpoint 6 for Fast Progressor Subgroup 1 and Endpoint 7 Fast Progressor Subgroup 2, the variable estimands depend on the outcomes for endpoints higher in the testing hierarchy.

- If both dose comparisons are statistically significant for all endpoints higher in the testing hierarchy, the active SYD-101 arms will be pooled for analysis of Endpoints 6 and 7, the annual progression rate for Fast Progressor Subgroup 1 and Fast Progression Subgroup 2, respectively.
 - The pooled comparison of SYD-101 to vehicle for Endpoint 6 will be performed at the retained alpha level of 0.05, and if statistically significant, the pooled comparison of SYD-010 to vehicle for Endpoint 7 will also be performed and assessed at $\alpha = 0.05$.
 - If both Endpoints 6 and 7 are statistically significant, then Endpoint 8 (axial length) each dose of SYD-101 will be compared to vehicle and the untruncated Hochberg procedure with $\alpha = 0.05$ will be used.
 - If Endpoint 6 (or Endpoint 7) is not statistically significant, then all subsequent endpoint(s) will be considered descriptive/nominal.

- If only one dose comparison was statistically significant for Endpoint 5, then only that dose of SYD-101 will be statistically compared to vehicle for Endpoint 6 and subsequent endpoints.)
 - The one dose comparison of SYD-101 to vehicle for Endpoint 6 will be performed at the retained alpha level of 0.005, and if statistically significant, the pooled comparison of SYD-101 to vehicle for Endpoint 7 will also be performed and assessed at $\alpha = 0.005$. The other dose comparison will be considered descriptive/nominal.
 - If both Endpoints 6 and 7 are statistically significant for the one dose comparison, then Endpoint 8 (axial length) will be compared to vehicle for that SYD-101 at $\alpha = 0.005$.
 - If Endpoint 6 (or Endpoint 7) is not statistically significant, then all subsequent endpoint(s) will be considered descriptive/nominal.

For the EMA submission, the key secondary endpoint will be the proportion of participants with myopic progression >0.75 D at or before Month 24. The analysis will use the same methodology as stated in Section **Error! Reference source not found..**

For the FDA submission, the key secondary endpoint will be the mean annual progression rate of myopia using data through Month 36. The analysis will use the same methodology as specified for this endpoint in Section **Error! Reference source not found..**

All other secondary endpoints will be analyzed at both Month 24 and Month 36 except for the Fast Progressor Subgroup 1 and Subgroup 2 analyses for the EU submission which is analyzed at Month 24. For Fast Progressor Subgroups 1 and 2, data after receipt of prohibited treatment or escape medication will be censored and multiple imputation will not be performed for this endpoint. The censoring and MMRM analysis methods will be utilized for study discontinuation (regardless of reason) and receipt of prohibited treatment or escape medication. The analyses at Month 24 will be considered the primary timepoint for assessment of secondary endpoints for the EMA submission with analyses generated at Month 36 being considered exploratory.

Conversely, the analyses at Month 36 will be considered the primary timepoint for assessment of secondary endpoints for the FDA submission, and the results generated at Month 24 being considered exploratory.

The mean change from baseline in axial length will be analyzed similar to the annual progression rate using a REML-based MMRM model including fixed effects for treatment group, baseline age category, categorical visit, and the treatment group by visit interaction, with baseline axial length as a covariate. No explicit structure will be assumed for the covariance among the repeated measures. However, in case there is a convergence problem with the unstructured covariance, then a compound symmetry covariance structure will be assumed. The Kenward-Roger Method will be used to calculate the denominator degrees of freedom for the test of fixed effects. For analysis at Month 24, all through Month 24 will be included in the model. Observations after receipt of prohibited treatment or escape therapy will be censored. Observations after treatment discontinuation will be included as observed. Multiple imputation will not be performed. A single average axial length for the right and left eyes will be used for analysis.

Proportionate progression rate endpoints using different cutoffs to define myopic progression (eg, ≤ 0.25 D/year, ≤ 0.50 D/year, and an increase of myopia of 0.50 D) will be analyzed similar to the primary endpoint using pairwise CMH tests; however, sensitivity analyses, other than PPS analyses, will not be performed.

Time to progression of myopia will be calculated in days as the date of first confirmed SE measurement that represents a reduction of >0.75 D or greater minus the date of first dose of study drug, plus one. Participants who do not experience myopic progression through 24 months (EMA) or 36 months (FDA) or who have an early discontinuation without a progression will be censored at the date of their last SE assessment at or before Month 24 (EMA) or Month 36 (FDA). Participants who receive a prohibited treatment or escape therapy prior to myopic progression will be censored as of the date they received the prohibited or escape therapy. Observations after treatment discontinuation will be included as observed. Each dose of SYD-101 will be compared to Vehicle for time to progression of myopia using the log-rank test stratified by the randomization stratification factors. Kaplan-Meier estimates of the distribution of time-to-event will be tabulated and plotted by treatment group. The tabulation will include the Kaplan-Meier estimate of the medians, 25th and 75th quartiles, and 95% CIs (if estimable). The number and percent of participants censored and with events will be presented.

For all secondary endpoints excepting axial length, time to progression, and the Fast Progression subgroups, intercurrent events will be handled as specified in [Table 3-5](#). Data will be multiple imputed assuming MAR for intermittent missing data. Observations after prohibited or escape treatments will be multiply imputed assuming MAR. Observations after discontinuation of treatment or study due to a related AE will be multiply imputed assuming MNAR using a sequential vehicle-based pattern regression. Observations after discontinuation of treatment or study not due to a related AE will be multiply imputed assuming MAR.

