9.1.2 SECONDARY EFFICACY ENDPOINTS

Refer to [Section 3](#) for definition and justification of endpoints.

The hypothesis testing of secondary endpoints will be conducted using a gatekeeping procedure based on a closed fixed-sequence test, provided the primary endpoint comparison is statistically significant. Additionally, the truncated Hochberg adjustment ($\gamma=0.80$) will be utilized to control for potential multiple dose comparisons for each endpoint. This procedure controls the study-wise type I error at the 0.05 significance level as described below.

In order to evaluate a dose comparison at each step, all preceding comparisons are to be statistically significant in favor of SYD-101 for that dose, ie, for a given endpoint, comparisons will only be

performed for the SYD-101 dose(s) that are statistically significant for the prior endpoint assessed. If both SYD-101 dose comparisons are statistically significant for the prior endpoint, the truncated Hochberg adjustment ($\gamma=0.80$) will be used to control type I error between the two doses for the given endpoint. Based on the truncated Hochberg adjustment with truncation parameter $\gamma=0.80$, if both dose comparisons were significant in the prior step, alpha of 0.05 is retained to the next step. In that step the truncated Hochberg adjustment will again be applied if there are two dose comparisons for the given step. However, if in the prior comparison, only one dose comparison of two comparisons was significant, then alpha of 0.005 is retained and the one dose comparison must yield a P value < 0.005 to be significant.

For the EMA submission, the SYD treatment arms will be combined and compared to vehicle for endpoints assessed on subset of fast progressors. For those endpoints, the one comparison will be assessed at the alpha level retained from the prior comparison (either 0.05 if both dose comparisons were significant for both doses for all prior endpoints assessed or 0.005 if only one dose comparison was significant for the prior endpoint assessed.)

Again, no correction for multiplicity for the different efficacy analysis for EMA and for FDA is required.

Table 9-4 summarizes all efficacy endpoints in order of testing for the EMA and FDA analyses.

Table 9-4: Order of Testing Efficacy Endpoint for EMA and FDA Analyses

| Endpoint | EMA | FDA |
|---|---|---|

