| 7. | 
Mean annual progression rate using Month 24 data on Subgroup of participants with refractive history of progression ≥ 0.5 D
 
If both dose comparisons are significant for prior endpoint, the SYD-101 0.01% and 0.03% arms will be combined for single comparison to vehicle at alpha retained from prior step. Otherwise, if only one treatment comparison is significant, then only that dose will be compared to vehicle using alpha retained from prior comparison
 | 
Mean change from baseline in axial length at Month 36 (at sites with the requisite equipment; at least 50% of participants)
 
Truncated Hochberg to control alpha for the two pairwise SYD to Vehicle comparisons
 |
| 8. | 
Mean annual progression rate using Month 24 data on Subgroup of participants with refractive history of progression ≥ 0.75 D
 
If both dose comparisons are significant for time to progression endpoint and the pooled dose comparison for prior endpoint was significant, the SYD-101 0.01% and 0.03% arms will be combined for single comparison to vehicle at alpha retained from prior step
 | |
| 9. | Mean change from baseline in axial length at Month 24 (at sites with the requisite equipment; at least 50% of participants) | |

| Endpoint | EMA | FDA |
|----------|---|-----|
| | Hochberg to control alpha for the two pairwise SYD to Vehicle comparisons | |

If the comparison is not statistically significant at any step, then remaining comparisons in the stated hierarchy will be considered nominal, descriptive, and exploratory. The study-wise type I error will be maintained with the above closed procedure. No type I error adjustment is required for the different primary endpoints between regulatory agencies as efficacy will be assessed independently in each submission.

Intercurrent events will be handled in the for the FDA and EMA key secondary estimands as presented in the table below.

Table 9-5: Summary of Intercurrent Event Handling for Key Secondary Estimands

| Intercurrent Event | Strategy for Key Secondary Estimands | Justification |
|---------------------------|---|--|
| Intermittent Missing Data | 
Hypothetical
 
 Intermittent missing data will be multiply imputed assuming data is missing at random (MAR) | Intermittent missing data are expected to be missing at random/due to logistical issues |

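### When only one dose survives the EMA hierarchy, the SAP and the protocol give conflicting rules on whether the fast-progressor endpoints test that dose alone or the two arms pooled

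*SAP*

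**What the plan says.** SAP Endpoints 6, 7 and 8 (Fast Progressor Subgroup 1, Fast Progressor Subgroup 2, axial length) are rows 7, 8 and 9 of Protocol Table 9-4. When both doses have passed everything above, the documents agree: the arms are pooled and tested at 0.05. The trouble is the branch in which only one dose has survived.

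SAP 8.2, in order:

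- The general one-dose rule, set out under the key secondary endpoint: "The dose comparisons for all subsequent endpoints of the significant dose will be assessed at 0.005". The other dose becomes descriptive from there on.
- The opening of the EMA one-dose branch: "then only that dose of SYD-101 will be statistically compared to vehicle for Endpoint 6 and subsequent endpoints".
- The next sub-bullet tests the one dose on Endpoint 6 at 0.005 and then, "if statistically significant, the pooled comparison of SYD-101 to vehicle for Endpoint 7 will also be performed and assessed at" 0.005. Its last sentence makes the other dose descriptive.
- The gate to Endpoint 8: "If both Endpoints 6 and 7 are statistically significant for the one dose comparison".

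Protocol 9.1.2:

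- The text says that "the SYD treatment arms will be combined and compared to vehicle for endpoints assessed on subset of fast progressors", and lists the level for that single comparison as 0.05, or "0.005 if only one dose comparison was significant for the prior endpoint assessed".
- Table 9-4 row 7: "if only one treatment comparison is significant, then only that dose will be compared to vehicle using alpha retained from prior comparison".
- Table 9-4 row 8 opens with "If both dose comparisons are significant for time to progression endpoint and the pooled dose comparison for prior endpoint was significant" and gives no rule for the case where only one dose has passed.

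**The concern.** For one foreseeable outcome the plan specifies two different hypothesis tests. The SAP's Endpoint 7 clause contradicts the rule that introduces it and the gate that follows it. A pooled test would also bring back into a confirmatory comparison a dose that the SAP has just declared descriptive. In the protocol, the text of 9.1.2 contradicts Table 9-4 row 7.

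Three things are at stake:

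- **Dilution.** If the failed dose has little effect, pooling hides a real effect of the surviving dose.
- **A broken gate.** A pooled Endpoint 7 result does not supply the single-dose result that the gate to Endpoint 8 asks for, so it is unclear whether axial length may be formally tested.
- **An open choice.** Under SAP 4.2 the data and randomization code go, after the Month 24 lock, to the team that runs the programs. Unless the text is settled first, the test could be chosen with the results in view.

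**Working it through.** **1. The plan's own thresholds.** With alpha 0.05 and gamma 0.80:

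- both doses significant: 0.05 × (1 + 0.80)/2 = 0.045
- one dose significant: 0.05/2 = 0.025
- alpha retained when one dose survives: 0.05 × (1 − 0.80)/2 = 0.005

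All three match the SAP. Every passage that gives a level for this branch leads to 0.005, so the level is not in dispute. What is in dispute is the comparison.

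**2. The rules side by side, one-dose branch.**

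| Source | Subgroup 1 (SAP Endpoint 6) | Subgroup 2 (SAP Endpoint 7) |
|---|---|---|
| SAP 8.2, opening rule | surviving dose | surviving dose |
| SAP 8.2, sub-bullet | surviving dose | pooled |
| SAP 8.2, gate to Endpoint 8 | surviving dose | surviving dose |
| Protocol 9.1.2, text on fast progressors | pooled | pooled |
| Protocol Table 9-4 | surviving dose (row 7) | no rule (row 8) |

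**3. Inputs for the size of the difference.** SAP 4.3.5 expects about 250 participants in Subgroup 1 and 200 in Subgroup 2. An even 1:1:1 split, assumed here, gives about 83 and 67 per arm. SAP 4.1 gives two sets of values: 0.65 − 0.325 = 0.325 D/year with SD 0.55 D (simulation), and 0.18 D/year with SD 0.60 D (sizing). Further assumptions: these trial-wide values hold in the subgroups, Subgroup 2 is nested in Subgroup 1, and no data are missing.

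**4. Unconditional power.** Two-sided 0.005, noncentral t, with λ = δ / (σ√(1/n₁ + 1/n₂)). For the pooled test, δ is the mean of the two doses' effects. With δ = 0.325 for the surviving dose and σ = 0.55:

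| Test | n | δ | λ | Power |
|---|---|---|---|---|
| Endpoint 6, single dose | 83 v 83 | 0.325 | 3.81 | 83.0% |
| Endpoint 7, single dose | 67 v 67 | 0.325 | 3.42 | 71.3% |
| Endpoint 7, pooled, failed dose inert | 134 v 67 | 0.1625 | 1.97 | 19.7% |
| Endpoint 7, pooled, failed dose at half effect | 134 v 67 | 0.24375 | 2.96 | 55.0% |

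If the failed dose has a fraction f of the surviving dose's effect, the two values of λ are equal when (1 + f)/2 = √(1.5/2) = 0.866, so f = 0.73. The extra degrees of freedom bring the break-even to about 0.72. Above that fraction pooling gains power; below it pooling loses power.

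**5. Given a passed Endpoint 6.** Endpoint 7 is reached only after Endpoint 6 succeeds, and the two share participants. In 200,000 simulated nested trials per scenario:

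| Scenario | Endpoint 6 passes | Endpoint 7 single | Endpoint 7 pooled | Opposite verdicts |
|---|---|---|---|---|
| 0.325 D, SD 0.55, failed dose inert | 83% | 84% | 21% | 63% |
| 0.325 D, SD 0.55, failed dose at half effect | 83% | 84% | 64% | 24% |

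The last three columns are conditional on passing Endpoint 6. A bivariate-normal check gives 84%, 23% and 65%. Its pooled figures are slightly higher because it ignores the gap between the two doses, which widens the SD of the pooled arm.

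With the sizing values (0.18 D, SD 0.60), Endpoint 6 passes only about 18% of the time. Given that, Endpoint 7 succeeds in about 61% (single), against 16% (pooled, inert) or 38% (pooled, half effect).

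**6. False claims.** If the surviving dose is truly null and the failed dose has the full 0.325 D effect, Endpoint 6 and a pooled Endpoint 7 are both rejected in favour of treatment in about 0.25% of trials. The Endpoint 6 gate sets that limit: 0.005/2 = 0.0025.

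**The case against.** The strongest reply is that this is a slip with an obvious reading. In SAP 8.2 the opening rule, the sentence making the other dose descriptive, the gate to Endpoint 8 and the general one-dose rule all point to the surviving dose. One word, probably carried over from the both-doses bullet, points the other way. Protocol 9.1.2 also has a general rule that a dose goes forward only if it was significant at the preceding endpoint, and Table 9-4 row 7 applies that rule to a fast-progressor endpoint. For Endpoint 6 the SAP and Table 9-4 agree.

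Most of that stands, and it shows which way to resolve the conflict. It does not remove the conflict. The protocol's paragraph on fast progressors separately ties 0.005 to a combined test, so someone arguing for pooling has support in both documents.

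The second reply concerns size. None of the figures conditions on how the trial came to have one surviving dose, and no probability of reaching the branch is given. In the 0.325 D scenario a half-effect dose (0.1625 D) would meet 0.045 on the primary about 93% of the time at 280 per arm, so the branch would mostly arise from a failure lower down, which is not modelled. With the sizing values, opposite Endpoint 7 verdicts after a passed Endpoint 6 occur in only about 9% (inert) or 6% (half effect) of all trials in the branch. These limits are real. The percentages describe what happens inside the branch, not how often the trial would enter it.

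**Conclusion.** The concern holds and should be fixed. For the case of one surviving dose, the SAP contradicts itself on Endpoint 7, the protocol contradicts itself on the first fast-progressor endpoint and gives no rule for the second, and the protocol text disagrees with the SAP's opening rule.

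The reach is narrow: EMA secondary Endpoints 6 to 8, in this branch only. A pooled test fixed in advance would not by itself inflate the type I error. Within the branch the choice is material. Under the 0.325 D scenario, Endpoint 7 power is 71% for the single dose against 20% to 55% pooled, for a failed dose with none to half of the effect. Pooling would help only if the failed dose kept more than about 72% of the surviving dose's effect. All of these figures rest on an even split, trial-wide effects and SDs applied to fast progressors, and complete data.

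**What to change.** Before the Month 24 unmasking:

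1. In the one-dose branch of SAP 8.2, replace the pooled Endpoint 7 comparison with a comparison of the same dose that was tested on Endpoint 6, at 0.005.
2. In the Protocol 9.1.2 text, limit the combining of arms to the case where both doses passed every prior endpoint, and delete the 0.005 alternative for the combined test.
3. In Protocol Table 9-4 row 8, add the one-dose rule in the same form as row 7.

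This follows the SAP's own opening rule, its Endpoint 8 gate and Table 9-4 row 7. It costs a few words in each document and needs no new data or operational change.

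A separate item can be settled in the same edit, though it adds no weight to this point. For axial length, the last FDA endpoint, Table 9-4 specifies truncated Hochberg, while SAP 8.2 specifies the untruncated version when both doses have passed everything. The cut-off for declaring both doses significant is therefore 0.045 in one document and 0.05 in the other.

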For the EMA submission, the fast progressors subset analyses of the mean annual progression rate of myopia using data through Month 24. The analysis will use the same methodology as specified for this endpoint in [Section 9.4.2](#) as for the EMA primary efficacy endpoint, however data after receipt of prohibited treatment or escape medication will be censored and multiple imputation will not be performed for this endpoint.

The mean change from baseline in axial length will be analyzed similarly to the annual progression rate of myopia as detailed in [Section 9.4.2](#) for the primary EMA analysis, however multiple imputation will not be performed and analysis of axial length will be performed on observed data only.

The testing procedure for multiple secondary endpoints is described in [Section 9.1](#).

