3.3. Secondary and Exploratory Efficacy Endpoints

The table below lists the secondary (key and other) efficacy endpoints and exploratory efficacy endpoints for the EMA and FDA submissions. The endpoints are listed in order of testing.

Table 3-3 Secondary Efficacy and Exploratory Endpoints

Endpoint	EMA	FDA
Key Secondary Efficacy Endpoint		
1.	Proportion of participants with myopic progression >0.75 D at or before Month 24	Mean annual progression rate of myopia through month 36
Other Secondary Efficacy Endpoints		
2.	Proportion of participants with annual myopia progression rate through Month 24 ≤ 0.50 D/year	Proportion of participants with annual myopia progression rate through Month 36 ≤ 0.50 D/year
3.	Proportion of participants with annual myopia progression rate through Month 24 ≤ 0.25 D/year	Proportion of participants with annual myopia progression rate through Month 36 ≤ 0.25 D/year
4.	Proportion of participants with increase of myopia of >0.50 D at or before Month 24	Proportion of participants with increase of myopia of >0.50 D at or before Month 36
5.	Time to progression of myopia of >0.75 D through Month 24	Time to progression of myopia of >0.75 D through Month 36
6.	Mean annual progression rate using Month 24 data on Subgroup of participants with refractive history of progression ≥ 0.5 D / year	Mean change from baseline in axial length at Month 36 (at sites with the requisite equipment; at least 50% of participants)
7.	Mean annual progression rate using Month 24 data on Subgroup of participants with refractive history of progression ≥ 0.75 D / year	
8.	Mean change from baseline in axial length at Month 24 (at sites with the requisite equipment; at least 50% of participants)	
Exploratory Efficacy Endpoints		
	Mean change from baseline in SE at Month 48 (ie, 12 months after randomized withdrawal)	Mean change from baseline in SE at Month 48 (ie, 12 months after randomized withdrawal)
	Mean time spent with selected activities	Mean time spent with selected activities
		Mean annual progression rate using Month 24 data on Subgroup of participants with refractive history of progression ≥ 0.5 D/year
		Mean annual progression rate using Month 24 data on Subgroup of participants with refractive history of progression ≥ 0.75 D/year

Key secondary and other secondary endpoints estimands will be based on the same target population and assessed under the same treatment conditions as the primary efficacy estimands.

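### The axial-length MMRM fits one age coefficient to a cumulative outcome, so part of the precision from age adjustment is lost at the tested visit

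*SAP*

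**What the plan says.** SAP 8.2 specifies the axial-length model in full: "fixed effects for treatment group, baseline age category, categorical visit, and the treatment group by visit interaction, with baseline axial length as a covariate". Age category and baseline axial length are main effects only, each with one coefficient shared by all visits.

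The model is carried over from the refraction endpoint. Protocol 9.4.3 says "The mean change from baseline in axial length will be analyzed similarly to the annual progression rate of myopia", and SAP 8.2 says the same ("The mean change from baseline in axial length will be analyzed similar to the annual progression rate"). The two outcomes are on different scales. SAP 8.1.1 divides the refraction change by elapsed days to give a yearly rate, whereas axial length is analysed as undivided change from baseline.

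On covariance, SAP 8.2 states "No explicit structure will be assumed for the covariance among the repeated measures"; if that fit does not converge, "then a compound symmetry covariance structure will be assumed". On missing axial-length data: "Multiple imputation will not be performed".

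Biometry is scheduled at Screening and Months 12, 24, 36 and 48 (Protocol 1.3). The tested visit is Month 24 for the EMA and Month 36 for the FDA, and axial length is the last secondary endpoint in both sequences (SAP 3.3). The model therefore has two post-baseline visits for the EMA test and three for the FDA test.

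**The concern.** If two age groups differ in axial growth by d mm per year, their mean changes differ by d at Month 12, 2d at Month 24 and 3d at Month 36. One coefficient cannot equal all three. For an annualised rate the difference would be d at every visit and one coefficient would fit, so the specification suits the endpoint it came from better than the one it was carried over to.

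Any age difference that the model does not absorb at the tested visit stays in the residual variance and enlarges the standard error of each SYD-101 versus Vehicle contrast. Age is a four-level randomization stratum covering 3 to 14 years (SAP 3.1), so the sponsor evidently expects it to be prognostic. Axial length is measured only at sites with the equipment and has no power statement. If only one dose survives the preceding tests, it is tested at 0.005 (SAP 8.2).

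**Working it through.** **The plan's own figures.** SAP 4.1 gives no power, SD or correlation for axial length. Its nearest statement concerns the annual progression rate: 280 per arm, difference 0.18 D, SD 0.60 D, two-sided alpha 0.025. The SE is 0.60 × √(2/280) = 0.0507, and 0.18/0.0507 − 2.241 = 1.31, which gives 90.5% power (90.3% with the exact noncentral t). That agrees with the stated >90% but says nothing about axial length.

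**Inputs from the documents.** Model terms and unstructured covariance (SAP 8.2); biometry schedule (Protocol 1.3); tested visits (SAP 3.3); 840 children allocated 1:1:1 (SAP 3.1). With axial length in at least half of them, that is 420 children, or 140 per arm.

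**Assumptions.** Age effect proportional to time; equal residual SD for each yearly increment; residual correlation φ between increments, varied from 0 to 0.9; complete data.

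**Step 1: where the single coefficient settles.** With residual covariance V and true age effects m at the visits, it converges to g = (1′V⁻¹m)/(1′V⁻¹1). Rewritten in yearly increments:

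- Month 24 analysis (two visits): g = (1 − φ)d
- Month 36 analysis, exchangeable increments: g = d(1 − φ)/(1 + φ)
- Month 36 analysis, AR(1) increments: g = (1 − φ)d

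The age effects actually needed are 2d and 3d.

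**Step 2: share of the age-adjustment gain lost.** This is ((m_T − g)/m_T)², where m_T is the age effect at the tested visit. At Month 24 it equals ((1 + φ)/2)². At Month 36 it equals ((3 − g/d)/3)².

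| φ | Month 24 | Month 36, exchangeable | Month 36, AR(1) |
|---|---|---|---|
| 0 | 25% | 44% | 44% |
| 0.3 | 42% | 67% | 59% |
| 0.5 | 56% | 79% | 69% |
| 0.7 | 72% | 89% | 81% |
| 0.8 | 81% | 93% | 87% |
| 0.9 | 90% | 97% | 93% |

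**Step 3: effect on the treatment contrast.** If age explains a fraction R² of final-visit variance, the variance ratio against a model with age by visit is 1 + (share lost) × R²/(1 − R²).

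- R² = 20%, factor 0.25. Month 24: 1 + 0.25 × 0.25 = 1.06 up to 1 + 0.90 × 0.25 = 1.23. Month 36: 1 + 0.444 × 0.25 = 1.11 up to 1 + 0.965 × 0.25 = 1.24.
- R² = 3%, factor 0.031. The ratio is 1.01 to 1.03 at both visits.

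In terms of the reported SE with 140 per arm, R² = 20% costs 140 − 140/1.0625 ≈ 8 to 140 − 140/1.226 ≈ 26 children per arm at Month 24. At Month 36 it costs 140 − 140/1.111 = 14 to 140 − 140/1.241 ≈ 27.

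**Step 4: simulation check.** The model was simulated with about 140 per arm, age-stratified arms, complete data, baseline axial length omitted and 300 runs per setting. For φ of 0.3, 0.5, 0.7 and 0.9, the share of the gain kept was about 0.57, 0.43, 0.25 and 0.06 at Month 24 (formula 0.58, 0.44, 0.28, 0.10). At Month 36 it was about 0.32, 0.20, 0.09 and 0.01 (exchangeable formula 0.33, 0.21, 0.11, 0.03).

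With age-balanced arms the two models gave the same treatment estimate; only the reported SE differed. At Month 24 with φ = 0.5 and R² = 25%, the reported SE was 0.2267 with the common age effect and 0.2075 with age by visit, against an actual SD of 0.2037 for both. Type I error with the common age effect was 0.02 to 0.06 across settings.

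**Step 5: the annual-rate model.** After division by time the age effect is d at every visit, so g = d and nothing is lost.

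**The case against.** A main-effects MMRM fixed in advance is a valid analysis. The result is unbiased, the SE errs on the safe side, the endpoint is last in both sequences, and no power was promised for it. All of that stands, and it makes this an efficiency point only.

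The size is not established by the documents. A reader might infer that nearly all the benefit of age adjustment disappears because the fitted age coefficient falls to about zero. That follows only if each child's growth is close to a straight line. For example, an assumed slope SD of 0.12 mm/year with measurement SD 0.03 mm gives φ = (0.0144 − 0.0009)/(0.0144 + 0.0018) = 0.83, hence 84% lost at Month 24. Year-to-year variation in growth lowers φ; at φ = 0.5 the Month 24 coefficient is half the Month 12 age effect. An age effect that slows also reduces the loss: with 20% slowing per year and φ of 0.5 to 0.9, it is 44-71% at Month 24 and 57-78% at Month 36.

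A reader might also take axial length to be the tested endpoint with the fewest children. The documents do not support this for the EMA: SAP 4.3.5 expects about 250 and 200 participants in the two fast-progressor subgroups, against 420 if half the sample has biometry. The half is itself a floor, and a footnote to the schedule in SAP 14.2 puts axial length at about 25%, so 140 per arm is an assumption.

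Finally, the calculations concern age alone. They do not show what a baseline-axial-length-by-visit term would gain.

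**Conclusion.** The point holds as a loss of precision. The model under-adjusts for age at Month 24 and Month 36, and the reported SE is larger than the collected data require. A substantial part of the age-adjustment gain goes, and possibly most of it at Month 36. The ranges above depend on proportional age effects, equal increment SDs, complete data and an undocumented increment correlation. Whether the loss matters depends on how much of the variation in axial growth age explains: it is negligible at 3% and worth recovering at 20%. There is no bias and no sign of type I error inflation. The figures apply to the unstructured covariance; the compound-symmetry fallback, which forces equal variance on a growing outcome, was not computed. The annual-rate MMRM needs no change on this ground.

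**What to change.** Before unmasking for the Month 24 analysis, amend SAP 8.2 to add a baseline-age-category-by-visit interaction to the axial-length MMRM, for both the Month 24 and the Month 36 analysis. A baseline-axial-length-by-visit term may be added on the same reasoning, with its gain unquantified.

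The cost is one line of SAP wording. With four age categories, the age interaction adds 3 × 1 = 3 parameters at Month 24 and 3 × 2 = 6 at Month 36; the baseline term would add 1 and 2 more. Against roughly 420 children that is minor. No new data are needed, and the estimand and testing order do not change. If age effects prove constant over visits, almost nothing is lost.
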